36. Partial Waiver of Consent for Screening/Recruitment.....	18
37. Partial Waiver of HIPAA Authorization for Screening/Recruitment.....	19
38. Waiver of Documentation of Consent.....	19
39. Alteration of Consent.....	19
40. Full Waiver of Consent/Parental Permission.....	20
41. Full Waiver of Consent/Parental Permission (Public Benefit or Service Programs).....	20
42. Full Waiver of HIPAA Authorization (Checklist).....	20
43. Other Waiver Types (Checklist).....	20

PROTOCOL TITLE: Dermatomal spread of Paravertebral and Erector Spinae Plane nerve blocks as compared by thermal imaging

44. Vulnerable Populations (Checklist).....20

45. Medical Devices (Checklist).....20

46. Export Control (Checklist)20

47. **Specimen Transfer/Sharing (Checklist) (required –do not delete even if the answer is “No”)**24

PROTOCOL TITLE: Dermatomal spread of Paravertebral and Erector Spinae Plane nerve blocks as compared by thermal imaging

1. Objectives

The objective of this study is to use thermal graphic imaging to objectively compare sensory nerve blockade distribution after placement of a Paravertebral peripheral nerve block vs. after placement of an Erector Spinae Plane block. Participants will receive both types of block (one per side), rather than one type on both sides. Both types are generally accepted, in common usage for this patient population, and applied frequently at UNM Outpatient and Imaging Services (OSIS) by investigators. Participants are drawn from a population that would already receive one or the other, depending on provider preference.

1.1. The investigators hypothesize that the two types of block procedures result in comparable anatomical distribution of effectiveness, as determined by thermal imaging.

2. Background

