Assessment of temperature change after Paravertebral block placement was first used in 1995 in a case series of six patients presenting for abdominal surgery. At this time, the Paravertebral blocks were placed using a landmark technique and thermal imaging was conducted using technology of the time. These authors used temperature changes as a surrogate marker of sympathetic and somatic nerve blockade.^{vi} A case study published in 2014 was specific to using thermal imaging to assess Paravertebral blockade in a patient presenting for breast surgery. Morznski et al. demonstrated this objective mapping of spinal nerve root blockade. He placed a unilateral landmark Paravertebral block and then using an infrared camera documented increases in temperature changes within the dermatomes of the blocked area.^{vii}

After a complete review of the literature, there have not been any articles to date that have been published using thermographic imaging to assess the efficacy of Erector Spinae Plane blocks. I purpose using thermographic imaging to assess dermatomal blockade of spinal nerves to compare the efficacy of Paravertebral nerve blocks versus the efficacy of blockade by placing an Erector Spinae Plane block. Based on the outcomes of this case series, further randomized controlled studies could be conducted to statistically compare the two blocks for the best analgesic blockade and if the two blocks are unequivocal this gives providers the ability to choose the safest of the two blocks.

[References are listed at the end of this protocol document]

PROTOCOL TITLE: Dermatomal spread of Paravertebral and Erector Spinae Plane nerve blocks as compared by thermal imaging

3. Study Design

This will be an unblinded case series of consenting patients serving as their own controls in a comparison of two commonly accepted nerve blockade techniques.

4. Inclusion and Exclusion Criteria

- 4.1. Potential participants will be identified from among investigators' usual patient caseload. The inclusion/exclusion criteria are simple, and will not require the recording of any PHI.

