- Individual participants will participate in the study for less than one hour after providing consent, including time for block placement, time for the blocks to take effect, and the thermal imaging.
- The investigators anticipate that all subjects can be enrolled within 12 months.
- Upon the completion of data collection, analysis and manuscript preparation are anticipated to take another five months.

7. Study Endpoints:

- 7.1. The primary outcome is the dermatomal distribution of skin temperature changes. No secondary outcomes have been identified.
- 7.2. The use of thermal imaging technology presents minimal risk to patients. In the unexpected event that an excessive number of patients experience block failure (in the opinion of the principal investigator), the investigators will stop enrollment. This is extremely unlikely, as both types of block are in common usage at OSIS with comparable success rates.
- 7.3. No exploratory endpoints have been identified.

8. Research Setting

- 8.1. Research activities will occur at the UNM HSC Outpatient Surgery and Imaging Services (OSIS) facility.
- 8.2. Physician-investigators on the study team will identify potential participants from among their usual patient caseload, using information already available to them. Recruitment will occur in the pre-operative holding areas of OSIS.
- 8.3. Recruitment, nerve block placement, and thermal imaging will occur in the pre-operative holding areas of OSIS. Post-recruitment analysis will occur in Anesthesiology department offices.
- 8.4. A community advisory board will not be used.

9. Resources Available

- 9.1. The PI ([name] MD) is a board-certified anesthesiologist at UNM. Her subspecialty area is regional anesthesia, where local anesthetics are used to provide surgical and analgesic pain relief by blocking nerve conduction of painful stimuli. She has supervised or personally placed over 10,000 peripheral nerve blocks in her career. She teaches and supervises anesthesiology residents and regional anesthesiology fellows in regional anesthesia. She even teaches at a national course for practicing anesthesiologists to learn regional anesthesia. [name] has been awarded sabbatical time to conduct this study by her department. She is the Medical Director of the Outpatient Surgical Center (OSIS) where the study will take place. She has intimate knowledge of the study site, procedures, and patient population. [name] will be responsible for all

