PROTOCOL TITLE: Dermatomal spread of Paravertebral and Erector Spinae Plane nerve blocks as compared by thermal imaging

anesthesia-related medical decisionmaking, and ordering and evaluation of any diagnostics or therapeutics that become necessary in context of the research.

9.2. *Describe other resources available to conduct the research: For example, as appropriate:*

- Approximately two patients per month presents to OSIS for bilateral mastectomy. Therefore, it is feasible that at least 12 patients can be recruited within 12 months.
- Facilities at OSIS are designed to accommodate regional-anesthesia procedures, which are a standard of care for bilateral mastectomies performed there.
- The Department of Anesthesiology has a thermal imaging camera (FLIR E95 42).
- OSIS has the facilities, supplies, personnel, and equipment necessary to respond to any situations arising from regional anesthesia procedures and mastectomy surgery.
- The PI will obtain all subjects' informed consent, perform their regional anesthesia procedures, and acquire thermal imaging. There is a small subset of regional anesthesiologists (approximately 6 attending physicians and 2 fellows) as well as midlevel, nursing, and resident physicians who will assist the PI in anesthesia-related matters outside the research, as in usual practice. While not performing research procedures per se, they will be made familiar with the research and its protocol-specified procedures.

10. Prior Approvals

10.1. The Departmental Review Form is included with this application.

11. Multi-Site Research

11.1. NA.

12. Study Procedures

[figure not shown]
12.1. Nearly all procedures described below are routine and within standard of care (SOC), with two exceptions performed for research purposes: the use of thermal imaging to evaluate nerve block distribution, and the application of different nerve block techniques (Erector Spinae Plane block on one side, and paravertebral block on the contralateral side) in the same patient. All participants are drawn from a population who would receive two blocks with the same technique, typically one of these two, regardless of the existence of this research project.

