12.2. Bilateral mastectomy patients will be identified before surgery. Informed consent will be obtained. In the preoperative holding area at OSIS, patient will be positioned in sitting position and a universal time-out will be performed. Patient will have surgical site marking by surgeon and regional site marking by regional anesthesiologist. The PI will randomly draw from a jar the side of the patient that the Paravertebral block will be placed on and the side that the Erector Spinae Plane block will be placed on. Patient will be administered sedation via IV for

PROTOCOL TITLE: Dermatomal spread of Paravertebral and Erector Spinae Plane nerve blocks as compared by thermal imaging

the procedure. Thermal imaging photographs will be obtained using the Flir E95 thermal imaging camera of the posterior, lateral and anterior thorax. The first of three sets of images will be obtained before regional anesthesia (nerve block) placement. Regional anesthesia will be performed as in usual practice for this patient population. The specifics of the block placement will not be modified from our usual practice for purposes of this research project. The patient will receive a Paravertebral block at T4 on one side and an Erector Spinae Plane block at T4 on the contralateral side under ultrasound guidance. Twenty minutes after the blocks are completed, thermal imaging photographs will be obtained of the posterior, lateral and anterior thorax. Ten minutes later another set of thermal imaging photographs will be obtained. The patient will then proceed to surgery. Ultrasound images are all saved under patient's MR per standard of care. Thermographic images will be saved on secure HSC servers under a sequential participant number for later review and analysis.

An example of the thermal image (from reference vii) is provided below:

13.Data Analysis

- 13.1. As this is a case series, formal statistical analysis beyond routine descriptive statistics is not appropriate.
- 13.2. As this is a case series, a power analysis is not appropriate.

14.Provisions to Monitor the Data to Ensure the Safety of Subjects

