- 16.12. Data will include thermal-imaging photographs, which will not include the facial area. These photographs use false color to depict skin surface temperature, and as such are different from typical photographs. Participants will be offered a look at the recorded images. Images will be deleted on participant request, and the participant will then be excluded from the study.
- 16.13. The research record will be maintained for at least 6 years after study completion.
- 16.14. Research records for this study will not involve minors, as they are excluded from participation.

17.Data and Specimen Banking

- 17.1. Data will not be banked for future use.

18.Risks to Subjects

- 18.1. Both of the regional anesthesia techniques under evaluation in this study are part of routine practice at UNM OSIS. The research does not modify any element of patient selection for regional anesthesia or details of placement. The only research-specific procedures are the use of two regional anesthesia techniques (rather than one) on consenting patients, and the recording of thermal imaging.
- 18.2. Peripheral nerve blocks like the ones used in this research are necessarily restricted to one side of the body and must be performed bilaterally for bilateral anesthesia. Therefore, some degree of risk of asymmetry in anesthesia effectiveness already exists regardless of the existence of this study. For that reason, it is difficult to evaluate the extent to which any risk of anesthesia asymmetry may be increased by this research, but it may exist; meaning that there is some small chance that a patient could have less pain control on one side. As noted in the consent, previously unknown risks or side effects also

PROTOCOL TITLE: Dermatomal spread of Paravertebral and Erector Spinae Plane nerve blocks as compared by thermal imaging

cannot be ruled out, but both techniques are well studied, so this is very unlikely.

- 18.3. The thermal images do not resemble normal photographs, but patients may experience unease while they are taken.
- 18.4. The only other risk identified by the investigators is that of breach of confidentiality, which exists in all research.
- 18.5. Both of the regional anesthetic techniques are well established with known safety profiles. Similarly, thermal imaging carries no known inherent risks. Therefore, it is unlikely that this research would carry any unforeseeable risks.

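### The only outcome has no stated metric or reference, and nothing hides the block side from whoever reads the stored images

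*Combined protocol and SAP*

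**What the plan says.** Section 1 sets the aim: to "use thermal graphic imaging to objectively compare sensory nerve blockade distribution" after the two blocks. Section 1.1 adds the hypothesis that the distributions are comparable. Section 3 puts it this way: "This will be an unblinded case series of consenting patients serving as their own controls in a comparison of two commonly accepted nerve blockade techniques".

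Section 7.1 gives one outcome: "The primary outcome is the dermatomal distribution of skin temperature changes". There are no secondary or exploratory endpoints (7.1, 7.3). Section 13.1 says that "formal statistical analysis beyond routine descriptive statistics is not appropriate".

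On who does what, section 9.2 has the PI obtain consent, "perform their regional anesthesia procedures, and acquire thermal imaging". Section 12.2 adds that "The PI will randomly draw from a jar the side of the patient that the Paravertebral block will be placed on". Image sets of the posterior, lateral and anterior thorax are taken before the blocks, 20 minutes after them, and 10 minutes after that. Then: "Thermographic images will be saved on secure HSC servers under a sequential participant number for later review and analysis". Section 16.9 limits access to the PI and study team, with legal and policy exceptions. Section 16.12 notes of the images: "These photographs use false color to depict skin surface temperature".

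**The concern.** Two gaps combine. First, the outcome names a thing to be described but not how it is measured. The plan does not say whether the result is a temperature change per dermatome, a map or a count. It does not say what the change is measured against, how dermatome regions are placed on the image, or how three views and two post-block sets are brought together. Second, no step hides the side when the stored images are read. The participant number conceals who the patient is, not which block went where, and the PI knows every allocation.

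The random draw protects the allocation of side. It does not protect the reading. A reader who knows the sides can settle borderline regions differently on the two sides, and if this follows an expectation it does not average out over patients. The expectation could run either way: section 1.1 expects comparable distributions, while section 2 calls the paravertebral block the gold standard.

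At stake is the word objective in the aim. Section 2 criticises earlier comparisons for relying on subjective measures. This map is the study's only result, and section 2 intends it to inform later randomised studies.

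**Working it through.** **Text check.** Sections 3, 7, 9.2, 12, 13 and 16 were set side by side. None gives a metric, a reference, a rule for placing dermatome regions, a named reader, or a masked, independent or duplicate reading. Section 12.2 provides a pre-block set, but the plan does not say that change is measured from it.

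**Figures in the plan.** There are none to reproduce: section 13.2 declines a power analysis and section 5.1 gives 6 complete cases without derivation. What follows is illustration. Every input except the 6 patients and the two post-block sets is assumed, and the counts apply only if dermatomes are scored as warmed or not warmed.

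**Model.** Ten dermatomes per side; n of them truly warmed by w; shared drift d on both sides; noise SD s for the change from baseline; cut-off c. Expected count on one side:

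count = n × P(N(w + d, s) > c) + (10 − n) × P(N(d, s) > c)

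**Reader effect.** Equal blocks (4 v 4), w = 1.0 C, s = 0.3 C, d = 0. The edge is read at c − 0.1 on one side and c + 0.1 on the other, a gap of 0.2 C.

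- c = 0.5: 4 × 0.977 + 6 × 0.091 = 4.46, against 4 × 0.909 + 6 × 0.023 = 3.77. False difference 0.68 (from unrounded values).
- c = 0.75: 3.60 against 2.78. False difference 0.82.
- c = 1.0: 2.53 against 1.48. False difference 1.05.

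Halving the gap to 0.1 C gives 0.33, 0.41 and 0.53. Over w = 0.6, 1.0 and 1.5 C, s = 0.2, 0.3 and 0.4 C and the same three cut-offs, the 0.2 C gap gives 0.01 to 1.53. With strong, sharp warming (w = 1.5, s = 0.2) it gives 0.13 at most.

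**Choosing afterwards.** 20,000 simulated series of 6 patients, no drift, independent noise in the two post-block sets. The figure is the mean spread (largest minus smallest) of the 6-patient average difference over cut-offs 0.5, 0.75 and 1.0 C and two sets, at s = 0.2 / 0.3 / 0.4 C.

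| Truly warmed | w = 1.0 C | w = 1.5 C |
|---|---|---|
| 4 v 4 | 0.96 / 1.13 / 1.27 | 0.17 / 0.58 / 0.89 |
| 5 v 3 | 1.47 / 1.49 / 1.46 | 0.17 / 0.59 / 0.90 |

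Part of this is noise between sets. With one fixed 0.5 C cut-off and w = 1.0 C, the two sets alone spread the 5 v 3 result by 0.15 / 0.43 / 0.63. At w = 1.0 C the top cut-off equals the true warming, so half the warmed dermatomes are missed there by construction.

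**Shared drift.** With 4 v 4 the two counts are identical, so the expected difference is 0 whatever d is. With 5 v 3 the difference is 2 × [P(N(w + d, s) > c) − P(N(d, s) > c)], which cannot exceed the true 2. At w = 1.0 and s = 0.3, raising d from 0 to 0.5 C moves it from 1.81 to 1.00 at c = 0.5, and from 1.00 to 1.81 at c = 1.0. The second move is towards the truth.

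**Precision of a left-right difference.** SD = s × √2 = 0.3 × 1.414 = 0.42 C per level. SE for 6 patients = 0.42 / √6 = 0.17 C (0.12 to 0.23 C for s = 0.2 to 0.4 C). This omits between-patient variation in block effect, so it is a lower bound.

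**The case against.** The strongest reply is that the outcome need not involve edges or counts at all. Section 7.1 speaks of the distribution of temperature changes, and a change per dermatome needs no cut-off. This stands: the defect is an unstated metric, and every count above is conditional on an analysis that the plan does not state. Someone still has to place the dermatome regions, so masking matters under either metric.

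Three stronger readings are tempting and should not be drawn.

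- A reader might infer that the PI will read the images knowing the sides. The documents name no reader; they only leave this open.
- A reader might infer from section 16.12 that dermatomes will be judged by colour. That section concerns confidentiality and explains how the images differ from ordinary photographs. The colour scale matters only if colour is used for reading.
- A reader might infer that warming common to both sides can exaggerate the difference between blocks. It cannot in expectation: it creates none between equal blocks and can only hide part of a true one.

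It is also fair that the study is openly declared unblinded, draws the side at random, is descriptive with 6 complete cases, and leaves statistical comparison to later trials. This lowers the stakes and excuses the missing power analysis. It does not excuse an undefined outcome, because sections 1 and 1.1 state a comparative aim and hypothesis. Finally, the step-shaped model has no gradual block edge and the 0.2 C gap is hypothetical, so the figures show what could happen and do not estimate what will.

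**Conclusion.** The point holds in this form: the sole outcome has no stated metric or reference, and nothing keeps the side from whoever reads the images, so the plan permits unmasked placement of regions and a metric chosen after the fact. That weakens the claim to an objective comparison.

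The size is uncertain. If counts against a cut-off are used, a modest side-specific shift could produce about one spurious dermatome under mid-range assumptions, and next to nothing when warming is strong and sharp. Choosing afterwards among three cut-offs and two sets could move a 6-patient result by about 1.0 to 1.3 dermatomes (4 v 4) or about 1.5 (5 v 3) at 1.0 C warming. The textual gap is certain; the magnitudes rest on assumed inputs. The study can proceed without the change, but should make it because it is cheap.

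**What to change.** Amend sections 7.1, 12.2 and 13.1.

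(a) **Masked reading.** An existing study-team member codes the stored images and mirrors a random half of the patients left to right, in the same way for all sets and views. Another existing team member, preferably one who did not place the blocks, marks the dermatome regions without the side allocation. All readings are locked before unmasking.

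(b) **Stated metric.** For each dermatome level and at both post-block times, report the paravertebral-minus-ESP difference in change from the pre-block image, using stored temperature values. It needs no cut-off and cancels drift equal on both sides. Show each side's own change from baseline beside it, because the difference alone cannot tell both warmed from neither warmed. If warmed/not-warmed maps are also shown, fix one cut-off and one temperature scale before any image is read.

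**Cost.** Probably a few hours of existing-team time, which matters in a small unfunded study (4.5). There are no extra patients, images or procedures, but temperature values must be kept with the images. Masking will be imperfect, since skin marks or puncture sites may show, and weak if the PI reads, having taken the images and perhaps recalling 6 cases. The left-right difference is noisier per level than one side's change, as shown above.

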- 4.2. Inclusion criteria: Participants will be drawn from adult female patients having bilateral mastectomy surgery over the age of 18.0 years, who consent to regional anesthesia for their postoperative pain relief. Exclusion criteria: Patients will not be enrolled if they are not yet 18 years old, unable to consent, using anticoagulant medication or have a bleeding disorder, are pregnant (all female patients of childbearing age who present for surgery already receive a urine pregnancy test for non-research reasons), or do not speak English.
- 4.3. Individuals from these protected groups will not be included in this research:
 - Adults unable to consent
 - Individuals who are not yet adults (infants, children, teenagers)
 - Pregnant women
 - Prisoners.
- 4.4. Male patients will be excluded. Bilateral mastectomy surgery is rare in this patient group, and any male patients who do present for such surgery are likely to be experiencing a clinical situation that is distinct from the typical bilateral-mastectomy population; potentially even idiopathic. Enrolled male participants may therefore have an untoward effect on the interpretation of study results, and will be excluded for that reason.
- 4.5. Non-English speakers will be excluded. This is a small unfunded study, and the cost of preparing suitable Spanish-language consent materials would present a substantial burden on the ability of the investigators to proceed. The investigators are not aware of any reason why language preference would affect study results or even correlate with other factors that may affect them, or why results from the contemplated sample could not be reliably extrapolated to patients who speak languages other than English.

5. Number of Subjects

- 5.1. A maximum of 12 participants will be recruited at this site. The planned case series size is 6 participants for whom complete data are available. The excess enrollment capacity is intended to accommodate any participants for whom the planned regional anesthesia techniques cannot be completed adequately. For example, poor ultrasound imaging or particular specifics of patient anatomy may lead to abandonment of an attempt to place regional anesthesia.

PROTOCOL TITLE: Dermatomal spread of Paravertebral and Erector Spinae Plane nerve blocks as compared by thermal imaging

6. Study Timelines

6.1. Describe:

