- 16.3. The research requires access to identifiers and PHI for inclusion screening and demographic purposes. The data to be used are not publicly available. The only element of the data that may be considered "sensitive" is the thermal imaging of the anterior thorax (chest) area of consenting participants. The thermal images do not resemble common photographs, but nonetheless necessarily include representations of adult women's breasts (see example in section 12). Other types of potentially sensitive data will not be sought or recorded.
- 16.4. Zip codes will not be recorded for research purposes.
- 16.5. The investigators do not plan to seek or obtain a Certificate of Confidentiality from the NIH.
- 16.6. Data will be secured by the use of electronic file storage on HSC secure servers, which are password-protected and feature numerous other security measures.
- 16.7. Data will be coded by sequential participant number.
- 16.8. The data to be collected are relatively minimal and the sample size is small, so quality control is not anticipated to be an issue. However, the linking sheet to MRN will permit any missing or unclear data to be checked and corrected as appropriate.
- 16.9. *Describe the following:*

PROTOCOL TITLE: Dermatomal spread of Paravertebral and Erector Spinae Plane nerve blocks as compared by thermal imaging

- The data will include the thermal images and basic demographic data: age, BMI, and surgical procedure.
 - Data will be stored in electronic format on secure HSC servers.
 - Data will be collected electronically from the FLIR camera and entered electronically in files stored on secure HSC servers.
 - Data will be stored for 6 years, as with all other study documentation.
 - Only the PI and study team members will have access to the data and study documentation, except as provided by law and HSC policy.
- 16.10. The main set of data (the thermal images) will be temporarily stored on the FLIR camera, before being transferred to a folder on the secure HSC network and deleted from the camera. The camera itself will be securely stored in a locked cabinet in Anesthesiology department offices.
- 16.11. Audio and video recordings will not be made or used.

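### The side draw takes no account of a diseased or previously treated breast, so in six self-controlled patients chance imbalance on that side could shift the comparison; a paired draw and recording the side would limit this cheaply.

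*Combined protocol and SAP*

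**What the plan says.** Section 12.2 (Study Procedures) sets the allocation: "The PI will randomly draw from a jar the side of the patient that the Paravertebral block will be placed on". The other side gets the other technique: "The patient will receive a Paravertebral block at T4 on one side and an Erector Spinae Plane block at T4 on the contralateral side". No stratification or blocking is described, and neither the jar's contents nor replacement of slips is stated.

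On eligibility, 4.2 says: "Participants will be drawn from adult female patients having bilateral mastectomy surgery over the age of 18.0 years". The exclusions do not mention one-sided disease, previous breast or chest surgery, or irradiation.

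The non-image data are set in 16.9: "The data will include the thermal images and basic demographic data: age, BMI, and surgical procedure". The affected side is not listed, and the surgical procedure need not identify it.

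On size, 5.1 says "The planned case series size is 6 participants for whom complete data are available" and "A maximum of 12 participants will be recruited at this site". The endpoint in 7.1 is: "The primary outcome is the dermatomal distribution of skin temperature changes". Each side has its own baseline, because 12.2 also says "The first of three sets of images will be obtained before regional anesthesia (nerve block) placement". Section 13 plans descriptive statistics only, with no adjustment for side.

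**The concern.** Using patients as their own controls (section 3) works cleanly when a patient's two sides differ only in the technique applied. The measurement rests on skin vessels: section 2 reasons from sympathetic block to vasodilatation to warming. If a diseased, operated or irradiated side has a different capacity to warm, the result on that side mixes technique with side. Subtracting the pre-block image removes a difference in starting temperature, but not a difference in response.

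Randomisation spreads this over the techniques in the long run. Six patients are too few to rely on that. The hypothesis in 1.1 is that the two distributions are comparable, so an imbalance that hides a difference matters as much as one that creates a false one. Because the affected side is not a planned data item, a reader of the results would have no planned way to see whether an imbalance had occurred.

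**Working it through.** The plan gives no power, effect size or imbalance figure, so there is nothing of its own to reproduce.

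**Inputs**
- Completed patients: 6 (5.1).
- One technique per side in each patient (12.2).
- Assumption: fair, independent draws, probability 0.5. The text does not settle this.
- Assumption: m of the six have one affected or previously treated side. The documents give no value, so m = 3 to 6 is shown.
- Assumption: after a block, the affected side's change differs from the other side's by a common d, in whatever unit the outcome is summarised. The documents do not give d, and it may be zero.

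**Formula.** Let k be the number of one-sided patients with the paravertebral block on the affected side. Each of these adds +d to the paravertebral-minus-erector-spinae difference. Each of the other m − k adds −d, and the remaining 6 − m add nothing. The sum is kd − (m − k)d = (2k − m)d, so the mean over six patients shifts by d × |2k − m|/6 in size. k follows Binomial(m, 0.5).

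**m = 6**

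| Split | Probability | Shift |
|---|---|---|
| 3–3 | 20/64 = 31% | 0 |
| 4–2 | 30/64 = 47% | 2/6 = 0.33d |
| 5–1 | 12/64 = 19% | 4/6 = 0.67d |
| 6–0 | 2/64 = 3% | 6/6 = 1.00d |

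A split of 5–1 or worse has probability 14/64 = 22%.

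**Fewer one-sided patients: chance that all fall the same way, 2/2^m**

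| m | Probability | Shift m/6 |
|---|---|---|
| 5 | 2/32 = 6% | 0.83d |
| 4 | 2/16 = 12.5% | 0.67d |
| 3 | 2/8 = 25% | 0.50d |

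As m falls, the largest possible shift gets smaller but becomes more likely.

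**If the jar is balanced left/right.** Suppose it holds three slips for each side, drawn without replacement, and three patients have left-sided and three right-sided disease. Let x be the number of left-sided patients drawing left. Then 3 − x right-sided patients also draw left, x draw right, and k = 2x. The probability of x is C(3,x) × C(3,3−x)/20. So k = 0 or 6 has probability 2/20 = 10%, and k = 2 or 4 has 18/20 = 90%. Balancing left and right does not balance the affected side.

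**The case against.** The strongest reply is that the documents do not show that an affected side responds differently to a block. Section 2 describes warming caused by the block and says nothing about diseased or treated skin. The images also cover the posterior and lateral thorax, where breast disease might matter less. This stands: d is an assumption, and the result can only be stated in units of d.

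Three stronger readings are tempting, and the documents do not support them.
- *The allocation is biased, and disease asymmetry will be reported as a technique effect.* A random draw is unbiased in expectation. The problem is chance imprecision in a descriptive series, and section 2 leaves statistical comparison to later randomised studies.
- *The draw is known to be unrestricted.* The text does not say so. The point survives, because a left/right-balanced jar would not help either.
- *An imbalance could never be found afterwards.* Section 16.8 keeps a sheet linking participants to their record number, and 16.2 notes that the treating physicians already have access. The item is unplanned, not unrecoverable.

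It can also be said that any series of six is unbalanced on many unlisted factors. That is true. What sets this factor apart is that it differs between the two sides being compared, is knowable before the draw, and costs almost nothing to balance.

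**Conclusion.** The point holds as a cheap improvement, not as a flaw that invalidates the comparison. The draw, the eligibility criteria and the data list all pass over the affected side. Under fair independent draws and a common d, a marked imbalance is a realistic outcome: 22% for 5–1 or worse if all six patients are one-sided, and 6% to 25% for a complete one-way split if five down to three are. The shifts range from 0.50d to 1.00d in those cases. Whether that matters depends on d and m, which the documents do not give. If d is zero, or every patient has symmetrical disease or none, there is no effect.

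**What to change.** **In 12.2**, before the first draw, keep a separate jar for patients with one affected or previously treated side. Draw without replacement from pairs of tickets, one reading *paravertebral on affected side* and the other *paravertebral on other side*. Return the ticket if the participant is replaced. Imbalance among completed one-sided patients is then at most about one patient, a shift of about d/6 = 0.17d. Use a simple left/right draw for everyone else.

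The separate jar matters. With one jar of six tickets (three of each kind) shared by all patients, and four of them one-sided, a 2–2 split has probability C(3,2) × C(3,2)/C(6,4) = 9/15 = 60%. The other 40% are 3–1, a shift of 0.33d.

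**In 16.9**, add affected side, and previous breast or chest surgery and irradiation by side. Check that 16.3, which limits the sensitive data collected, still agrees. Show each patient's result by affected side. This part is worth doing even if the paired draw is declined.

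**Cost and downside.** The cost is a few tickets and some chart items already open to the team. The second draw of each pair is predictable to the unblinded principal investigator, who under 9.2 also obtains consent and places the blocks, and section 15 allows patients to be withdrawn. So log each draw when it is made, and every later withdrawal with its reason. Balance limits the shift; it does not guarantee zero if d varies between patients.
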